### **4.3 Study Flow**

- Upon arrival at the study site, potential candidate will be required to complete a CRF (Case Report Form) to verify subject eligibility. If found eligible, the subject

[figure not shown]
will be provided information about the study and consented to participate in the study.

- Subject will be provided with Dario BGMS Welcome Kit, Dario Test Strip Cartridges, lancets and Control Solutions.
- Subject will download the App and register and will conduct the first Dario measurement in the clinic
- Subject will be handed with Coach communication channels page (including coach name, phone number and email address\_
- At this stage the subject has completed the first clinic visit of the study and can start the coaching program.
- The Diabetes health coach will be provided subject's information and will set up the first phone call coaching session with the subject.
- Before the first session the coach will receive a subset of the CRF with the subjects relevant information.
- During the first session, the Diabetes health coach will complete an intake session which includes aspects in Diabetes quality of. The questions express the satisfaction of the patient with managing and controlling diabetes. The items were added according to specific quality of life module ("Development of diabetes-specific quality of life module to be in conjunction with the World Health Organization quality of life scale brief version (WHOQOL-BREF)" Lin et al. *Health and Quality of Life Outcomes* (2017) 15:167). The Diabetes health coach will set up phone calls with the subject on a basis of two times per month for a period of three months.
- During the entire coaching period of three months the Diabetes health coach will have two coaching sessions a months (a total of six session throughout the program) and also will communicate via various communication channels: chat, SMS, email and phone and will drive the coaching based on the data captured by Dario Application including: blood glucose measurements, physical activity, carbs etc. Each coaching session will be recorded in a dedicated coaching summary form as provided in appendix B.
- Following the three months coaching the coach will have a closing session with the subject which will include progress, satisfaction and quality of life questions.
- On day 91 to day 100 the subject will be required to arrive at the Name of Clinic for a venous blood sample administered by a nurse/technician for testing:
  - HbA1C

- Lipid panel: Total Cholesterol, Triglyceride, LDL and HDL levels
- HCT

The nurse will measure weigh Body Mass Index and Blood Pressure.

- The subject is then released from the study.
- The flowchart below illustrates the study flow:

## **5.0 Study Population**

### **5.1 Inclusion Criteria**

To be eligible to participate in this study, a subject must meet all the following criteria:

7. Adults 35 years of age or older
8. Diagnosed type 2 Diabetes
9. HbA1C test taken less than 2 months ago and is equal to or above 8.5%
10. Able to read, write and understand English
11. Have supported smartphone (see appendix C for the full smartphone list) with internet package for their service provider
12. The subject is able and agrees to sign the informed consent form

### **5.2 Exclusion Criteria**

A potential subject who meets any of the following criteria will be excluded from participation in this study:

8. Adults with impaired cognition
9. Cohabiting with a participant in the study
10. Have an underlying medical condition (such as kidney disease, hemoglobin variants, anemia) that may provide misleading A1C levels
11. Subject is critically ill
12. Subject has an impairment that prevents him/her from following the study procedures
13. Subject is not using medication that may interfere with the blood glucose measurement
14. HCT level which are outside Dario BGMS declared range (20%-60%)

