Data to be Collected:	
 
• QoL questions
 
• Demographic (age, gender, ethnicity, education, etc.)
 
• Diabetes profile: type, time since diagnosis and insulin treatment
 
• Concomitant medications
 
• Medical history
 
• Dario measurement details (test strip lot #, smart mobile device type, Dario meter #)
 
• Capillary whole blood Glucose levels
 
• Venous blood test: HbA1C, Lipid profile, HCT results
 
• Blood Pressure (BP)
 

Inclusion / Exclusion Criteria	
Inclusion Criteria
 
 
1. Adults 35 years of age or older
 
2. Diagnosed type 2 Diabetes
 
3. HbA1C test taken less than 2 months ago and is equal to or above 8.5%
 
4. Able to read, write and understand English
 
5. Have supported smartphone (see appendix C for the full smartphone list) with internet package for their service provider
 
6. The subject is able and agrees to sign the informed consent form
 
 
Exclusion Criteria
 
 
1. Adults with impaired cognition
 

	
 
2. Cohabiting with a participant in the study
 
3. Have an underlying medical condition (such as kidney disease, hemoglobin variants, anemia) that may provide misleading A1C levels
 
4. Subject is critically ill
 
5. Subject has an impairment that prevents him/her from following the study procedures
 
6. Subject is not using medication that may interfere with the blood glucose measurement
 
7. HCT level which are outside Dario BGMS declared range (20%-60%)
 

Analyses & Reports:	Complete analysis and final report after enrolling up to 25 subjects and aiming to have 20 people running the full three months program (after withdrawal) to complete the coaching program that meet the inclusion/exclusion criteria

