## **4.0 Study Design and Procedure**

### **4.1 Study Description**

This study is designed to assess the effect of digital self-monitoring platform used with the remote support of a Health coach on clinical outcomes and Diabetes quality of life. Study design will be an open-label randomized trial of adults with Type 2. Patients are recruited through the Diabetes and Endocrinology Consultants center setting. Upon randomization to the intervention group, study participants will receive three months diabetes health coaching comprising of:

1. Two scheduled phone sessions with a Diabetes health coach a month;
2. Ongoing dual communication with the coach using digital communication channels such as chat, SMS and emails
3. Diabetes education, behavior modification, goal setting and reinforcement.

The Dario App will record participant's glucose measurements and additional information captured by the patient such as medication intake, food and physical activity results. The coach will get access to the patients' App captured information and will intervene ad necessary in the context of the clinical information.

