### **4.2 Study Outcome measures**

The following outcomes will be evaluated on subjects that completed the three month coaching program at the end of study vs. baseline.

1. Wellness
  - a. Quality of Life evaluation by questionnaires
2. Clinical outcome
  - a. HbA1C taken in blood test
  - b. Capillary Blood Glucose
  - c. Weight and BMI
  - d. Cardiovascular risk parameters, Lipid panel: Total Cholesterol, Triglyceride, LDL and HDL levels – Blood test
  - e. Blood Pressure

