### **5.3 Recruitment**

The study is aimed to recruit a total of 25 male and female subjects having Type 2 Diabetes between ages 35 years or older. The recruitment will be performed through the Diabetes and Endocrinology Consultants of Pennsylvania, LLC (Decpa LLC) center. The clinic will identify patients that have done HbA1C test during the last 60 days and has HbA1C level as indicated in the inclusion criteria. These subjects will be approached by the clinic to participate in the study.

Each subject completes the study in 2 visits to the diabetes and endocrinology consultants center. The subject will receive a Diabetes health coaching which will include 2 monthly coaching sessions for a period of three months. The total study duration depends on the ability to enroll 25 subjects and is planned for three to four months.

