## **9.0 Statistical Analysis**

### **9.1 Sample Size**

This study will include up to 25 subjects.

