## **9.2 Data Analyses**

Data will be analyzed comparing the quality of life and clinical outcome before and after the program.

To assess the outcome of the study, the effect of intervention along with digital self-monitoring will be evaluated. Paired group tests will be applied for comparing the results gathered on the same subjects after three months to the baseline values.

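### No exclusion in 5.2 is aimed at pregnancy, bariatric surgery or another trial, so weight, BMI, lipids and blood pressure are unguarded in a before-after analysis of about 20 completers (minor)

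*Combined protocol and SAP*

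**What the plan says.** Section 5.2 lists seven exclusions, numbered 8 to 14, which the synopsis repeats as 1 to 7. Item 10 is the one on confounding conditions: "Have an underlying medical condition (such as kidney disease, hemoglobin variants, anemia) that may provide misleading A1C levels". Items 13 and 14 concern the glucose measurement (interfering medication, and hematocrit outside the meter's range). Items 8, 9, 11 and 12 cover impaired cognition, cohabitation with another participant, critical illness, and impairments that prevent the study procedures.

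Section 5.3 plans to "recruit a total of 25 male and female subjects having Type 2 Diabetes between ages 35 years or older".

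The outcomes in section 4.2 go well beyond glycemia. They include "Weight and BMI", four lipids and blood pressure, as well as quality of life, HbA1c and capillary glucose.

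On analysis, section 9.2 says "Paired group tests will be applied for comparing the results gathered on the same subjects after three months to the baseline values". Section 4.2 restricts this to completers: "The following outcomes will be evaluated on subjects that completed the three month coaching program at the end of study vs. baseline". Section 9.1 says "This study will include up to 25 subjects", and the synopsis adds "aiming to have 20 people running the full three months program". The synopsis calls the design single-arm, whereas section 4.1 says "Study design will be an open-label randomized trial of adults with Type 2".

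**The concern.** The sponsor accepted the principle that a condition able to distort an outcome should be screened out, but applied it only to glycemic measurement. Counting the four lipids separately and blood pressure once, section 4.2 names ten measures. Seven of them (weight, BMI, four lipids, blood pressure) have no entry rule aimed at protecting them.

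Pregnancy, bariatric surgery shortly before or during follow-up, and a treatment given in another trial can each move one or more of these measures within three months, whatever the coaching does. A comparison with the subject's own baseline has no way to separate such a change from the program's effect. With about 20 pairs, one extreme value shifts the mean and also inflates the SD. The reported change may then be exaggerated, or a real change hidden. The plan gives no outlier rule and no sensitivity analysis that would expose it.

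**Working it through.** **What the plan fixes.** Enrolment is up to 25 (9.1) and 20 completers are aimed for (synopsis). These agree with 20% loss: 1 - 20/25 = 0.20, and 20/(1 - 0.20) = 25. The documents give no SD, effect size, alpha or power, so every input below other than n is an assumption.

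**Search of the criteria.** Sections 5.1 and 5.2 and the synopsis copy do not name pregnancy, bariatric surgery or concurrent trial participation. Nor does the rest of the supplied text.

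**Formulas.** One subject whose change exceeds the others' mean by D shifts the mean of n pairs by D/n. If the other n - 1 subjects have SD s, the total sum of squares is (n - 2)s² + ((n - 1)/n)D². Take n = 20 and s = 3 kg; the two-sided 5% t value on 19 df is 2.093.

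**Reference case, no unusual subject.** SE = 3/√20 = 0.671 kg; half-width = 2.093 × 0.671 = 1.40 kg.

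**One subject at -20 kg, the others averaging 0.**
- Mean: -20/20 = -1.0 kg (-20/25 = -0.8 kg if all 25 complete).
- SS = 18 × 9 + 0.95 × 400 = 542; SD = √(542/19) = 5.34 kg.
- Half-width = 2.093 × 5.34/√20 = 2.50 kg, giving a 95% interval of about -3.5 to +1.5 kg.

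**One subject at +10 kg, the others averaging -2 kg.**
- Mean: (19 × -2 + 10)/20 = -1.4 kg.
- D = 12, so SS = 162 + 0.95 × 144 = 298.8; SD = √(298.8/19) = 3.97 kg.
- t = -1.4/(3.97/√20) = -1.58. Without that subject's excess, t = -2/0.671 = -2.98. A significant result becomes a non-significant one.

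**Range for weight.** Excess losses of 10, 20 and 30 kg shift the mean by 0.5, 1.0 and 1.5 kg at n = 20.

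**Range for HbA1c.** One subject with an excess change of 2, 3 or 4 points shifts the mean by 0.10, 0.15 or 0.20 points. With an SD of change of 1.0 to 2.0, the SE is 0.22 to 0.45, so the shift is about 0.2 to 0.9 SE.

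**Chance of a false significant decrease.** This was simulated with 100,000 paired t-tests per setting, n = 20 and no true effect; the nominal one-sided rate is 2.5%.
- Weight, SD 3 to 5 kg, one subject with 15 or 25 kg excess loss: 1.0% to 4.4%.
- HbA1c, SD 1.0 to 1.5, excess decrease of 2 to 4 points: about 4.0% to 4.5% with one such subject, and about 6% to 8.5% with two.

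The rate stays near nominal with one subject because the outlier inflates the SD as well as moving the mean.

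**The case against.** The strongest reply is that any unusual subject is influential at n = 20, that the three conditions are the reviewer's selection, and that every magnitude above is assumed. That is fair, and it limits the priority. The documents do not say how often such subjects would present, and nothing shows that the center runs other interventional studies.

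Three stronger readings are tempting, and the documents do not support them.

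- A reader might infer that the exclusion list protects only HbA1c and meter readings. It does not: items 8, 9, 11 and 12 serve other purposes. Nor does item 13 protect meter readings as written, because it excludes subjects who are not using interfering medication, which reverses its evident purpose.
- A reader might infer that all such subjects are certain to be admitted. Item 10 gives examples rather than a closed list, so an investigator could apply it to pregnancy if A1C were judged misleading. It does not clearly reach surgery, and it does not reach another trial. The screening form in Appendix A is not reproduced, so relevant questions may already be there, although sections 5.1 and 5.2 set eligibility.
- A reader might infer that the study is certainly uncontrolled. The synopsis and 9.2 say so in effect, but 4.1 describes randomization and must be reconciled with them. Even then, the comparison planned in 9.2 is only with baseline.

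Medical history and concomitant medications are collected, so some affected subjects could be identified afterwards. That makes a sensitivity analysis feasible, but the plan does not include one. Withdrawal under 6.2 is no substitute. It rests on the subject's best interest or inability to comply, and a withdrawn subject drops out of the completer analysis.

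**Conclusion.** The point holds as a minor one. No criterion is aimed at protecting weight, BMI, lipids or blood pressure from a large change unrelated to the program, and the planned analysis would count that change as program effect.

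The most likely harm is a distorted mean and a wider interval, or a masked real effect. It would be wrong to conclude that one such subject would produce a spurious positive finding. In the -20 kg example t is -1.0/(5.34/√20) = -0.84, far from significance, and the simulated error rates support the same conclusion.

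The sizes rest on 20 completers, an assumed SD of 3 kg among the others, and assumed changes of -20 and +10 kg. In 25 recruits the frequency of such subjects is probably low, but that is a judgment; the documents give no figure.

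**What to change.** Add three exclusions to section 5.2 and the synopsis:

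1. pregnancy, or pregnancy planned during the study;
2. bariatric surgery planned before the day 91-100 visit, or performed recently, within a window that the sponsor sets;
3. concurrent participation in another interventional study.

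Ask about these in the screening questionnaire (6.1) if the Appendix A form does not already do so. Add to 9.2 that if one of these arises after entry, a subject with end-of-study data stays in the analysis, and each affected outcome is reported with and without that subject. In the same amendment, reconcile the design wording in 4.1 with the synopsis and 9.2, and correct the reversed wording of item 13.

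The cost is a short amendment and up to three screening questions. The downside is a few lost candidates and a slightly narrower population.

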### 6.3 Medical Information

Demographic and medical information acquired verbally from the subject and through the screening questionnaire – including (but not limited to) age, gender, relevant medical information, concomitant medications, etc. – will be recorded in the CRF for all subjects participating in this study.

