## 7.4 Protocol Deviation

Any deviation from the study protocol should be notified to the sponsor and fully documented on study deviation forms. Situations where the investigator anticipates, contemplates or makes a conscious decision to deviate from the protocol must be approved by the sponsor prior to deviation. Situations where unforeseen circumstances are beyond the control of the investigator's control (product failure, patient illness, etc.) and/or where the investigator needs to protect the subject's life or physical well-being in an emergency do not require prior sponsor approval.

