## 7.5 Protocol Modification

An amendment to the protocol may be proposed to the sponsor by the clinical site staff. The amendment will be prepared and approved by the sponsor. The amendment must be

---

 According to 21 CFR 812.3(k), blood sampling that involves simple venipuncture is considered noninvasive.

submitted to the IRB. When applicable, the amendment's implementation will take place only once approved by the IRB.

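### The exclusion criterion on interfering medication is reversed in both the synopsis and section 5.2: as written, it excludes subjects who do not use such medication

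*Combined protocol and SAP*

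**What the plan says.** Section 5.2 opens with the rule for its list: "A potential subject who meets any of the following criteria will be excluded from participation in this study". Item 13 is then "Subject is not using medication that may interfere with the blood glucose measurement". The same sentence is item 6 under the exclusion heading of the Protocol Synopsis.

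The meter readings are used in two ways. Section 4.2 lists "Capillary Blood Glucose" as outcome 2b. Section 4.3 says that the coach "will drive the coaching based on the data captured by Dario Application including: blood glucose measurements".

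Section 6.1 places the screening questionnaire in Appendix A. Only the heading of that appendix is in the text available for review, so how the question is put to candidates cannot be seen.

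**The concern.** In an exclusion list, meeting an item removes the candidate. A sentence saying that the subject is *not* using interfering medication describes a suitable candidate, so here it removes the people the trial wants and passes those it evidently means to keep out. The error is in an operative eligibility rule, and the two places that state the rule agree with each other, so comparing synopsis with body would not reveal it.

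The site has two courses, and neither is satisfactory:

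- **It follows the text.** Everyone who passes this item uses medication that may disturb the meter. Outcome 2b and the readings that steer the coaching become potentially unreliable.
- **It follows the evident intent.** Each enrolled subject who uses no such medication meets a written exclusion criterion. Section 7.4 asks that any deviation be notified to the sponsor and documented, and says that a situation in which the investigator "makes a conscious decision to deviate from the protocol must be approved by the sponsor prior to deviation".

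The synopsis also describes its target of 20 completers as people who satisfy the eligibility criteria. A reversed criterion makes it unclear who counts toward that number.

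**Working it through.** The plan gives no figure to reproduce here. The check is one of logic, followed by two simple counts.

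**1. Apply the section 5.2 rule to item 13.**

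| Candidate | Meets item 13 as written? | Result under the section 5.2 rule |
|---|---|---|
| Uses no interfering medication | Yes | Excluded |
| Uses interfering medication | No | Not excluded by this item |

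The synopsis has no such opening sentence, but its exclusion heading gives the same result for item 6.

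**2. Compare with the other items.** Each list has seven exclusion items. The other six are impaired cognition, living with another participant, a condition that may distort A1C, critical illness, an impairment that prevents following the procedures, and hematocrit outside the meter's 20% to 60% range. In all six, the presence of the problem excludes. Items 10 (A1C) and 14 (hematocrit) protect the validity of a measurement, which is evidently the purpose of item 13 too.

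**3. Look for a correction elsewhere.** The sentence would make sense as an inclusion criterion. However, the six inclusion items in the synopsis and the same six in section 5.1 contain nothing on medication. No other section in the available text restates or corrects the rule.

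**4. Rule out a text-extraction fault.** The same complete, grammatical sentence appears in two separate places. A word inserted by accident when the file was read is not a plausible explanation.

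**5. Count what is exposed.**

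- *Outcomes.* Section 4.2 has lettered items 1a, 2a, 2b, 2c, 2d and 2e, which makes 6. Only 2b is read from the meter, so 1 of 6.
- *Subjects.* Section 9.1 allows up to 25. If all are enrolled by intent and none uses interfering medication, at most 25 × 1 = 25 subjects meet the written exclusion criterion.

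The documents do not say how many candidates use interfering medication, so no share of the population can be estimated.

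**The case against.** The strongest reply is that nobody would be misled. The intent is plain from the neighbouring items, and a specialist diabetes clinic is unlikely to seek out candidates whose medication disturbs the meter. The Appendix A form, which cannot be seen, may already ask the question the right way round. A site that reads the item in its evident sense is arguably not making a conscious decision to deviate, so the prior-approval clause of section 7.4 may not apply. The two counts are also modest evidence: 25 is only the enrolment ceiling, and 1 of 6 depends on counting lettered items, since 2c holds two measures and 2d holds four lipids.

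Much of this is fair. There is no evidence that the literal rule was or would be applied. The figure of 25 is an upper bound, not an expected harm, and 1 of 6 describes scope rather than the size of any bias. Whether prior approval is needed can be argued either way, although the duty in section 7.4 to notify and document covers any deviation.

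None of this rescues the wording. An eligibility criterion has to be usable as written, and this one serves its purpose only if the reader ignores what it says.

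**Conclusion.** The criterion is wrong as written, in both places, and must be corrected. Confidence in the wording error is high because it follows directly from the section 5.2 opening rule. That the reversal is unintended is an inference, though a strong one, from the other six items and from the lack of any medication item among the inclusion criteria.

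The direct effect is limited to capillary glucose and the meter-driven coaching. HbA1C, lipids, weight and BMI, blood pressure and quality of life are not measured with the meter. No sample size, power or significance level is affected. The practical effect on enrolment is unknown, because it depends on the unseen screening form and on how many candidates use such medication.

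**What to change.** - **Wording.** Delete *not* from synopsis exclusion item 6 and section 5.2 item 13, so that use of potentially interfering medication is what excludes. Moving the unchanged sentence to both inclusion lists would give the same rule, but deleting one word is simpler.
- **Screening form.** Check that the medication question in Appendix A runs in the same direction.
- **Subjects already enrolled, if any.** Compare their concomitant medications with the corrected item. Section 6.3 says that this information "will be recorded in the CRF for all subjects participating in this study". The available text does not name the medications that interfere, so the check needs a stated source. The device User Guide listed in section 2.5 is a place to look, but its content is not shown.
- **Approval.** Section 7.5 requires the amendment to be submitted to the IRB and says that, when applicable, its "implementation will take place only once approved by the IRB".

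The cost is one word in two places, a check of one form and an IRB submission. Visits, procedures and analyses do not change.
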